7.7.6.1.1 Routine tests

Table 7-2 shows the routine hematology test, blood chemistry test, and urinalysis parameters.

Table 7-2. Routine laboratory tests

Classification	Parameter
Hematology	Leukocyte count, erythrocyte count, hemoglobin, hematocrit, leukocyte fractions (eosinophils, basophils, neutrophils, monocytes, lymphocytes), platelet count
Blood chemistry	AST, ALT, LDH, γ -GTP, ALP, creatine kinase, total bilirubin, total protein, blood urea nitrogen, serum creatinine, uric acid, total cholesterol, triglycerides, Na, K, Cl, Ca, blood glucose, HbA1c ^a , TSH ^a , FT3 ^a , FT4 ^a
Urinalysis (qualitative)	Urinary protein, urinary glucose, urobilinogen, urinary occult blood

a For new subjects, measurements will be obtained at Visit 1 only.

7.7.6.1.2 Pregnancy test

Pregnancy will be determined by the test for human chorionic gonadotropin (HCG) in urine or serum (only with post-menarchic females) at Visits 1 (or Visit 2 for consecutive subjects) and 18 (or at discontinuation of the tapering period; if not transferred to the tapering period, at completion or discontinuation of the treatment period [Visit 17]). For consecutive subjects, a measurement at Visit 9 in the preceding study may be used as a measurement at Visit 2 of this study.

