Study design: This study is a multicenter, open-label, uncontrolled, long-term treatment study in children and adolescent patients with depressive disorder. This study will include a total of 135 patients; consecutive subjects who have completed the preceding study "Phase-3 clinical study of duloxetine hydrochloride in children and adolescent patients with depressive disorder: Superiority study versus placebo" (Study No.: 1701A3631) then wish to continue the study treatment will be enrolled, as well as additional subjects who have child and adolescent depressive disorder, with a target of 100 subjects completing a 1-year treatment.
This study will consist of the following four periods (a total of 53 to 56 weeks): screening period (1 to 3 weeks), treatment period (50 weeks), tapering period (1 to 2 weeks), and follow-up period (1 week). Note that consecutive subjects will undergo three periods (a total of 52 to 53 weeks), excluding the screening period. New subjects whose eligibility has been confirmed after obtaining informed consent will be pre-registered (Visit 1), and, after completion of the 1- to 3-week screening period, their eligibility will be confirmed again and they will be registered (Visit 2).

Consecutive subjects will give consent for this study before completing the observation at Visit 9 in the preceding study, and, after completing the observation at Visit 9 in the preceding study and the eligibility of this study is confirmed, be enrolled in this study from Visit 2 (registration).

After registration, the study drug will be administered orally, once daily after breakfast.

Study subjects: The subjects must meet the following criteria: (i) aged ≥ 9 to <18 at the time of obtaining consent and assent (consecutive subjects are allowed to be enrolled if they are aged ≥ 9 to <18 in the preceding study); (ii) diagnosed as having depression or persistent depressive disorder as defined in the Diagnostic and Statistical Manual of Mental Disorders, version 5 (DSM-5), with onset at the age of ≥ 7 ; and (iii) fully meeting the criteria for a depressive episode. The Mini-International Neuropsychiatric Interview for Children and Adolescents (MINI-KID; version 7.0.2) will be used for diagnosis on the basis of DSM-5.

Inclusion/exclusion criteria:	Subjects must meet all the following criteria:	Consecutive subjects	New subjects
	Inclusion criteria		

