4.2 Inclusion criteria

Subjects must meet all the following criteria:

Inclusion criteria	Consecutive subjects	New subjects
1) Have completed a 7-week treatment in the preceding study and wish to continue treatment with duloxetine.	X	
2) Have been diagnosed with depression or persistent depressive disorder, as defined in the Diagnostic and Statistical Manual of Mental Disorders, version 5 (DSM-5), and fully meet the criteria for a depressive episode. MINI-KID (version 7.0.2) is used for diagnosis of depression.		X
3) Are aged ≥ 9 to <18 at the time of obtaining consent and assent, and must have been ≥ 7 at the initial onset of depression episode. Are male or female and are hospitalized or out-patients.		X
4) Have a legal representative capable of providing written informed consent for this study. In addition, for patients aged ≥ 13 , a written, informed assent must also be obtained from the patient him/herself. For patients aged ≥ 9 to <13 , a written, informed assent should also be obtained from the patient him/herself if possible.	X	X
5) For post-menarchic females, a pregnancy test result must be negative at Visit 1 (or Visit 2 for consecutive subjects). In addition, the patient must agree to use one of the following contraceptive methods from Visit 1 (or Visit 2 for consecutive subjects) until 1 month after the final administration. However, this requirement does not apply to females for whom it can be confirmed in writing that 6 weeks or more has passed since bilateral ovariectomy. Estrogen- and progesterone-containing, combined-hormonal contraceptive agents with ovulation-suppressing effects (administered orally, intravaginally, subcutaneously, etc.), progesterone-containing hormonal contraceptive agents (administered orally, intravenously, by implantation, etc.), intrauterine device, intrauterine system, bilateral tubal ligation, male	X	X

Inclusion criteria	Consecutive subjects	New subjects
partner's vasectomy, or sexual abstinence.		
6) The principal investigator or sub-investigator judges that the subject's legal representative can ensure that the subject him/herself will comply with all hospital visits, tests, and other procedures stipulated in this protocol. In addition, the principal investigator or sub-investigator judges that the subject him/herself will be able to comply with all the hospital visits, tests, and other procedures stipulated in this protocol.		X

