22) Judged by the principal investigator or sub-investigator to have the complication of substance-related and/or addictive disorders, as defined in DSM-5, or a history of such disorders. However, patients with caffeine-related disorder can be enrolled.		X
23) One or more substances of abuse (phencyclidines, benzodiazepines,		X

Exclusion criteria	Consecutive subjects	New subjects
cocaine-type drugs, stimulants, cannabis, opioids, barbiturates, tricyclic antidepressants, etc.) detected by urinary drug screening at Visit 2.		
24) Intension to travel overseas between Visit 1 (or Visit 2 for consecutive subjects) and Visit 6.	X	X
25) Pregnant* or possibly pregnant, breastfeeding, hoping to become pregnant during the study period. Or recently given birth. * Pregnancy: Pregnancy tests (blood or urine human chorionic gonadotropin) will be performed in all post-menarchic females.	X	X
26) Previously administered the study drug during participation in this study, or during participation in a different clinical study on duloxetine.		X
27) Have received another study drug within 30 days before Visit 1 or are currently receiving it.		X
28) Participation judged to be inappropriate for any other reason by the principal investigator or sub-investigator.	X	X

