5.2 Dosage and regimen

All subjects will receive oral duloxetine once daily after breakfast for 51 or 52 weeks (a 50-week treatment period and 1- to 2-week tapering period) from the day after registration (Visit 2). Note that, once or twice between Visits 5 and 17, the subjects should visit the study site without taking a dose to collect a blood sample for pre-dose PK (refer to Section 7.6). Table 5-1 shows the treatment regimens for the study drug. During the treatment period, the subjects will receive duloxetine 20 mg/day for one week then 40 mg/day for one week, and subsequently receive either 40 mg/day or 60 mg/day for 48 weeks as appropriate.

Subjects who complete the treatment period or who withdraw from it during Week 2 or later of treatment period will be transferred to the tapering period. During the tapering period, subjects whose duloxetine dose at discontinuation or completion of the treatment period is 60 mg/day will receive 40 mg/day for one week then 20 mg/day for one week. Subjects whose duloxetine dose at discontinuation or completion of the treatment period is 40 mg/day will receive 20 mg/day for one week. However, tapered administration may be omitted if serious adverse drug reactions occur, there are safety-related problems, or the subject or his/her legal representative refuses the tapered administration.

Table 5-1. Treatment Regimens

Treatment period			Tapering period	
Week 1	Week 2	Weeks 3 - 50	Week 51	Week 52
20 mg/day	40 mg/day	60 mg/day	40 mg/day	20 mg/day
1 x 20 mg LY248686 capsule	2 x 20 mg LY248686 capsule	3 x 20 mg LY248686 capsule	2 x 20 mg LY248686 capsule	1 x 20 mg LY248686 capsule
		40 mg/day	20 mg/day	-
		2 x 20 mg LY248686 capsule	1 x 20 mg LY248686 capsule	-

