7.2 Confirmation of demographic factors and medical history

(1) Baseline subject characteristic and medical history

For new subjects, the following baseline subject characteristics will be obtained at Visit 1 and entered in the CRF: date of birth; sex; height; ethnicity; race; hospitalization status; history of current condition (age at onset of depression, number of depressive episodes to date, timing of onset of current episode); disease category according to DSM-5; and medical history. As to medical history, important aspects of medical history necessitating hospitalization and/or surgery, all complications continuing as of the time of obtaining informed consent, and surgical history are determined.

For consecutive subjects, the baseline subject characteristics and medical history will be based on the information obtained in the CRF of the preceding study.

(2) Urinary drug screening

For new subjects, urinary drug tests will be performed at Visit 2, and the presence or absence of substances of abuse (phencyclidine, benzodiazepines, cocaine-type drugs, stimulants, cannabis, opioids, barbiturates, tricyclic antidepressants, etc.) will be determined.

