7.7.6 Laboratory tests

7.7.6.1 Laboratory test items

At Visits 1 (or Visit 2 for consecutive subjects), 5, 8, 11, 14, and 18 (or at discontinuation of the tapering period; if not transferred to the tapering period, at completion or discontinuation [Visit 17] of the treatment period), blood samples will be collected for laboratory tests, the volumes being 2 mL for hematology tests, and 8 mL and 5 mL for blood chemistry tests, at Visit 1 and other visits, respectively; and urine samples will also be collected. The samples will then be sent to the clinical laboratory facility specified in Section 7.7.6.2. Details of the collection, handling, storage, and shipment of samples are stipulated in a separate document. For new subjects, blood samples and urine samples at Visit 1 will be collected after obtaining informed consent, between 3 weeks before the initial administration of the study drug and Visit 2. For consecutive subjects, a measurement at Visit 9 in the preceding study may be used as a measurement at Visit 2 of this study. Both new subjects and consecutive subjects will be registered after the latest measurements at Visit 2 are confirmed.

The principal investigator or sub-investigator will judge whether the abnormal change from baseline (i.e., Visit 1 for new subjects or Visit 2 for consecutive subjects) is clinically significant (refer to Section 7.7.7.7), and will record any changes judged to be clinically significant as adverse events. The sample collection dates will be recorded in the CRF for each sample type (blood or urine).

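### New post-menarchic subjects need no pregnancy test at Visit 2, so the re-check of the pregnancy exclusion at registration can rest on a result about three weeks old

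*Protocol*

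**What the plan says.** Three places in the protocol set the entry pregnancy test, and they agree:

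- Section 4.2, criterion 5: "a pregnancy test result must be negative at Visit 1 (or Visit 2 for consecutive subjects".
- Section 7.7.6.1.2: testing applies "only with post-menarchic females) at Visits 1 (or Visit 2 for consecutive subjects) and 18", with discontinuation or Visit 17 as the alternative to Visit 18. A Visit 9 result from the preceding study may serve as the Visit 2 result for consecutive subjects.
- Appendix 1: the Visit 1 test carries the footnote for new subjects only, and the Visit 2 test the footnote for consecutive subjects only. SAP Appendix 1 repeats this schedule.

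Section 4.3, criterion 25, excludes in both cohorts anyone "Pregnant* or possibly pregnant, breastfeeding, hoping to become pregnant during the study period". Its note adds that "Pregnancy tests (blood or urine human chorionic gonadotropin) will be performed in all post-menarchic females", without naming a visit. For new subjects the Overview says that after screening "their eligibility will be confirmed again and they will be registered (Visit 2"). Dosing starts "from the day after registration (Visit 2"), according to section 5.2.

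**The concern.** Pregnancy status can change, or become detectable, during a screening period of 1 to 3 weeks. Several other entry criteria for new subjects use information gathered at Visit 2: the C-SSRS answers (criterion 12), body weight (criterion 13) and the urine drug screen (criterion 23). Pregnancy is not among them, although urine is already collected that day: "For new subjects, urinary drug tests will be performed at Visit 2" (section 7.2).

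A pregnancy too early to show at Visit 1 can therefore pass criterion 5, pass the Visit 2 re-check on the same old result, and be exposed to study drug. Pregnancy is both an exclusion (criterion 25) and a reason for discontinuation (section 4.5), so the plan itself treats this exposure as one to avoid.

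**Working it through.** **Inputs**

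- Visit 1 falls on Day -21 to -7, with registration (Visit 2) on Day 0 (Table 7-3).
- The first dose is on the day after registration, Day 1 (section 5.2).
- New subjects' Visit 1 blood and urine may be collected "between 3 weeks before the initial administration of the study drug and Visit 2" (section 7.7.6.1).
- Consecutive subjects have no screening period and register within 3 days after the last dose of the preceding study (section 3.1; Appendix 1, footnote c).

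**Step 1: the plan's own days.** Weeks -3 to -1 give -3 × 7 = -21 and -1 × 7 = -7. This matches Table 7-3.

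**Step 2: age of a result obtained on the Visit 1 date.** Age is reference day minus test day.

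- At registration: 0 - (-7) = 7 days to 0 - (-21) = 21 days.
- At first dose: 1 - (-7) = 8 days to 1 - (-21) = 22 days.

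**Step 3: age if the section 7.7.6.1 window also covers the pregnancy sample.** Section 7.7.6.1.2 is nested under 7.7.6.1, so this is a possible reading, but the text does not say so. The earliest sample is then on Day 1 - 21 = Day -20, which is 21 days old at first dose. The latest is on Day 0, which is 1 day old. The range is 1 to 21 days.

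Under either reading a result about 3 weeks old complies. The window permits a fresher sample but does not require one.

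**Step 4: with a Visit 2 test.** The result is 1 - 0 = 1 day old at first dose.

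**Step 5: what a Visit 2 test adds for conceptions before Visit 1.** These are the ones that contraception from Visit 1 cannot address. Let L be the lag in days from conception to a positive test, and g the days from the Visit 1 test to Visit 2. The Visit 1 test misses conceptions in the L days before it. A Visit 2 test misses only those in the L days before Visit 2. Of the L missed days before Visit 1, it recovers min(g, L). The documents give no value for L, so I assume 7, 14 and 21 days to show the range:

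| | g = 7 | g = 14 | g = 21 |
|---|---|---|---|
| L = 7 | 7 of 7 | 7 of 7 | 7 of 7 |
| L = 14 | 7 of 14 | 14 of 14 | 14 of 14 |
| L = 21 | 7 of 21 | 14 of 21 | 21 of 21 |

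**Step 6: the other cohort.** Consecutive subjects' result belongs to Visit 2 or to Visit 9 of the preceding study, and they move straight from Visit 9 to registration. The 3-day limit runs from the last dose and not from the test, so it is not an exact bound on the age of the result. There is still no gap comparable to 7 to 21 days of screening.

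**The case against.** The case for leaving the schedule alone is that it is consistent and already has several safeguards. Criterion 5 requires one of the listed contraceptive methods, which include abstinence, from Visit 1. There is a physical examination at every visit, and subjects are told to stop the drug and report a pregnancy at once. Section 7.7.6.1 also has both cohorts registered only after the latest measurements at Visit 2 are confirmed. All of this stands and keeps expected cases few. It does not close the gap: contraception from Visit 1 cannot act on a conception before Visit 1, and the latest measurement can be the three-week-old one.

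A reader might draw four stronger conclusions that the documents do not support:

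- *That the pregnancy exclusion is not confirmed at entry.* Appendix 1 marks confirmation of the criteria at Visit 2, and criterion 25 extends to possible pregnancy, which leaves room for the investigator's judgement. Only a repeat test is missing.
- *That the protocol contradicts itself.* Criterion 5, section 7.7.6.1.2 and Appendix 1 agree.
- *That consecutive subjects are always tested afresh at registration.* They may use the Visit 9 result, so the difference between cohorts is one of degree.
- *That the long wait for the next scheduled test argues for a Visit 2 test.* Visit 18 is nominally on Day 350 + 7 = 357 or 350 + 14 = 364, whether or not a Visit 2 test is added. That interval is the same for completers in both cohorts, and subjects who discontinue are tested at discontinuation.

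**Conclusion.** The point holds as a modest design gap. For new post-menarchic subjects the only required entry test is tied to Visit 1. The result may be up to 22 days old at first dose if obtained on the Visit 1 date, or up to 21 days if the section 7.7.6.1 window applies. A Visit 2 test would reduce this to 1 day.

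The benefit rests on some detection lag existing; its length is assumed, and the table shows how much it matters. The documents do not give the number of new post-menarchic subjects or a pregnancy rate, so I do not estimate a count beyond saying that it should be small. No endpoint, analysis set or sample-size figure is affected. The change is worth making because it checks an existing exclusion just before exposure at little cost.

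**What to change.** In criterion 5 (section 4.2 and the Overview), section 7.7.6.1.2 and Appendix 1, require the pregnancy result used at the Visit 2 eligibility confirmation to be current at Visit 2 for both cohorts. For new post-menarchic subjects, do this by also reading hCG on the urine already collected for drug screening. Keep the Visit 1 test, state whether a Visit 9 result counts as current for consecutive subjects, and align SAP Appendix 1.

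The cost is one urine hCG reading per new post-menarchic subject, which is below the 135 planned registrations because that total includes consecutive subjects. No extra visit or blood draw is needed. The sponsor should check that sample handling, which section 7.7.6.2 leaves to a separate document, allows a result before registration. Criterion 23 already makes eligibility depend on the Visit 2 urine drug screen, so a similar turnaround should be feasible, but the documents do not confirm it for hCG.

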7.7.6.2 Methods for collection, storage, and shipment of samples

An principal investigator, sub-investigator, nurse, or medical technician will collect blood and urine samples at the stipulated times, and send them to the below clinical laboratory facility. Details of the collection, handling, storage, and shipment of samples are specified in a separate document.

7.7.7 Evaluation of adverse events

7.7.7.1 Evaluation methods for adverse events

An adverse event is any unfavorable medical event suffered by someone administered a pharmaceutical product (including a study drug) and does not necessarily have a causal relationship with the relevant pharmaceutical product. In other words, an adverse event is any unfavorable and/or unexpected sign (including abnormal laboratory test result), symptom, or disease associated with the administration of a drug, irrespective of any causal relationship with that drug. Surgery that was already planned is not considered to be an adverse event, unless it leads to exacerbation of an existing disease, and is therefore not considered to be a serious adverse event even if it necessitates hospitalization. However, if an additional surgery is performed in connection with the planned surgery, this is taken to be an adverse event, and to be a serious adverse event if prolongation of hospitalization is required, or if any other criterion for being a serious adverse event is met. Hospitalization or prolongation of hospitalization for reasons other than adverse events is not considered to constitute a serious adverse event.

The presence or absence of an adverse event will be confirmed on the basis of the subject's spontaneous complaint, non-inductive questions, examination, C-SSRS, blood pressure, pulse rate, body weight, and ECG or laboratory test results. Adverse events include new onset of an event, increase in the severity or frequency of an event since administration initiation, and diagnostic abnormality, including abnormal laboratory test results. A symptom recorded as a medical history at study initiation will be handled as an adverse event only when symptoms are aggravated. In addition, loss of efficacy, and changes in the primary disease (depression) or scores for any of the CDRS-R items, will not be handled as adverse events in this study, unless judged to be serious adverse events.

The principal investigator or sub-investigator will evaluate adverse events. The principal investigator or sub-investigator will carefully investigate each adverse event, and record in the CRF the date of onset, time of onset, date of cessation (if the outcome is recovery or death), severity, seriousness (including the reason for judging seriousness), causal relationship with the study drug, actions taken for the adverse event, and outcome of the adverse event.

7.7.7.2 Assessment period

Adverse events occurring between obtaining the legal representative's informed consent (for new subjects) or initiation of study drug administration in this study (for consecutive subjects) and 7 days after the final administration of study drug (the follow-up period) as well as adverse events consecutive from the preceding study at the initiation of study drug administration in this study (only if applicable) will be assessed. For consecutive subjects, adverse events that occurred between obtaining informed consent for this study and initiation of study drug administration in this study will be assessed in the preceding study. In the case of withdrawn subjects, the principal investigator or sub-investigator will assess adverse events up to 7 days after final administration of the study drug. Appropriate follow-up will be continued until one of the following, and the outcome will be determined on that basis: (i) the relevant adverse event recovers to the pre-administration state (if consecutive from the preceding study, it should be recovered to the pre-administration of the preceding study); (ii) the subject's condition stabilizes or becomes chronic; (iii) the subject is lost to follow-up; or (iv) the principal investigator or sub-investigator judges further assessment to be unnecessary. In addition, if the subject stops visiting hospital during the study, he/she will be followed up by an appropriate method such as by telephone, and the findings will be entered in the CRF.

If the above adverse event follow-up has to be continued for 28 days or more after completion of administration, the outcome at the earliest date after 28 days after completion of administration will be recorded in the CRF.

